9.2.2. Age and Dates

Age will be presented as the number of years between date of birth and the reference date. The following age in Table 2 may be computed, with reference date indicated.

Table 2: Age and Reference Date

| Age | Reference Date |
|---------------------|----------------------------|
| • Age at enrollment | • Date of informed consent |

The following formula should be followed for calculation of age if needed:

$$\text{Age (year)} = \text{FLOOR}(\text{reference date} - \text{date of birth})/365.25$$

where FLOOR() function returns the integer part of the result.

In cases where only the month and year are provided for a date, the day for the date will be imputed as 15. Missing month will be imputed as June. In cases where the day is observed but

the month is missing, the date will be imputed as June 15. In instances when the imputed reference date is earlier than the birth date, the birth date will be used as the reference date.

9.2.3. Analysis Relative Day

Analysis relative day is the day relative to the first dosing day. It will be calculated as: analysis date – first dose date + 1 if analysis date is after the first dose date, or else as: first dose date – analysis date.

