7.3. Copper and Molybdenum Balance Analyses

The primary objective of this study is to assess the change from Baseline in Cu balance over 2 weeks of repeated daily ALXN1840 dosing (ALXN1840 treatment at 30 mg/day in healthy participants). Secondly, the study will also assess whether a net negative Cu balance is achieved following ALXN1840 treatment. The study will also assess Mo balance at ALXN1840 PK steady state.

Copper balance is defined by the difference in Cu input and Cu output. A negative Cu balance will indicate greater Cu output than Cu intake. Copper input is defined as the sum of all Cu input as measured in all food and fluids over the specified period. Copper output will be defined as the sum of all Cu output as measured in urine and feces over the specified collection period. Many of the Cu inputs and outputs will be collected with technical replicates and the mean of the replicates will be utilized in the analysis. Daily balance values may also be calculated. The study assumes insensible Cu/Mo loss due to sweat does not change significantly with ALXN1840 treatment and is therefore not measured.

Molybdenum mass balance is defined as the difference in Mo input and Mo output. It will be calculated in a similar manner as Cu balance and includes the additional Mo intake from ALXN1840. The nominal amount of Mo contained in ALXN1840 will be used and is estimated as 3.33 mg in each 15 mg tablet per the following calculation: 95.96 g/mol (molecular weight of Mo) / 432.54 g/mol (molecular weight of bis-choline tetrathiomolybdate) * 15 mg/tablet = 3.33 mg Mo. Mo mass balance will be calculated at steady state (Day 12 through Day 15) and over the entire Treatment Period (Day 1 through Day 30).

The average daily Cu and Mo balance, and/or change from Baseline in average daily Cu and Mo balance will be calculated using data from the following periods:

- Day -4 through Day -1 representing the Pre-dose Baseline Period (Cu/Mo balance)
- Days 4 through Day 15 representing the 30 mg/day Treatment Period (Cu balance for primary and secondary endpoints)
- Day 1 through Day 15 representing the ALXN1840 30 mg/day Treatment Period (Mo mass balance and Cu as exploratory analyses)
- Days 12 through Day 15 representing the Steady State Treatment Period (steady state Mo/Cu balance)
- Days 1 through Day 30 representing the entire Treatment and Post-treatment Period (total Mo and Cu balance)

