As ALXN1840 is expected to increase Cu removal through fecal excretion, Cu in stool will be critical for determining Cu balance. Because stools can be irregular, assessment of Cu and Mo

balance will only include data up to the day of the final bowel movement. For example, if for the Day 1 through Day 15 collection period, the final bowel movement occurs on Day 14, average daily Cu balance for the Day 1 through Day 15 period will only include data averaged from Day 1 through Day 14 (and Day 15 data will be omitted).

In the case of the 30 mg/day Steady State Treatment Period for Mo balance, fecal data collected on Days 16 and 17 may be used if needed to support assessments for the 30 mg/day Mo steady state balance. Use of this fecal data (as needed) is consistent with an approximately 2-day gastrointestinal transit time.

In the case of bowel movement irregularity and to support assessment of Cu output over time, bowel movement Cu and Mo outputs may be averaged over the days between bowel movements (or start of study) to ensure an approximate value for each 24-hour period as needed for calculations. The 24-hour collection period is defined as relative to the first ALXN1840 dose administration.

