7.4.1. Study Duration, Treatment Compliance, and Exposure

Study duration will be summarized for all enrolled participants by group and overall. Study duration is defined as the time from first dose to the EOS or study discontinuation date (whichever occurs first) + 1.

Compliance to the study treatment regimen will be determined as the days taken / the days expected to be taken during the treatment period x 100. Treatment compliance will be summarized using descriptive statistics by group. If a patient discontinues prematurely from the study, his or her compliance will be based on the period up to the point of discontinuation from the study. Compliance will also be summarized using counts and percentages by compliance category (i.e., $\geq 100\%$ compliance, 80 to $<100\%$ compliance, 60 to $<80\%$ compliance, etc.).

Exposure will be summarized for the Safety Set by group and overall. The duration (days) of exposure to treatment will be calculated as date of last exposure to treatment – date of first dose + 1. The actual duration of treatment will be calculated as the exposure period – number of days on which treatment was temporarily stopped. The duration of exposure, average daily dose (mg), minimum daily dose (mg) and maximum daily dose (mg) will be summarized using descriptive statistics. A supportive listing will also be provided.

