7.4.3. Other Safety

7.4.3.1. Analyses for Laboratory Tests

Actual values and changes from treatment Baseline (eg, chemistry, blood cell count with differential, and urinalysis) will be summarized descriptively for participants with available data for each laboratory parameter by group and overall. Missing laboratory data will not be imputed and only scheduled assessments will be included in by-visit summaries. All data, including that which is only collected at Screening, will be included in data listings. Laboratory measurements will be listed separately by participant, laboratory test, unit, and visit.

Where applicable, laboratory results will be classified as “low,” “normal,” or “high” with respect to the parameter-specific reference ranges (ie, below the lower limit of the normal range, within the normal range, or above the upper limit of the normal range). Contingency tables will be presented for each laboratory parameter to summarize the shift from the Baseline category to all

visits and to the worst post-Baseline measurement, defined as the value numerically farthest outside of the normal range across all post-Baseline visits through the end of the study.

Summary results for shift will include the count and percentage of participants within each shift category by scheduled visit. Laboratory values outside the normal range will also be summarized and assessed for trends indicating a safety signal. Additionally, a summary and listing of liver enzyme elevation will be presented and an evaluation of drug-induced serious hepatotoxicity plot will be created.

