9.2.8. Visit Windowing

In analysis of data summarized by study visit, all data collection will be reassigned a study visit where data is scheduled for collection based on the actual days relative to Baseline. All visits will be assigned a target study day. Baseline will have a target study day of 1. For each assessment, the post-Baseline period will be divided up using the scheduled visit's target day.

The lower bound of each visit interval will be evaluated as the mid-point between the target day and the previous visit's target day in the following manner: study day interval lower bound = ceiling(target study day - ((target study day - last target study day)/2)). Table 3 shows an example of visit windowing that will be used to summarize by-visit vital sign data. Other data will be summarized similarly in accordance to their SoA (Protocol Table 1).

Table 3: Visit Windows Used to Summarize By-visit Vital Signs Data

| Scheduled Visit | Target Study Day | Study Day Interval |
|-----------------|------------------|--|
| Baseline | 1 | Last measurement on or prior to first dose of study drug |
| Day 2 | 2 | 2 to 3 |
| Day 5 | 5 | 4 to 6 |
| Day 8 | 8 | 7 to 9 |
| Day 11 | 11 | 10 to 12 |
| Day 14 | 14 | 13 to 14 |
| Day 15 | 15 | 15+ |

If more than 1 value is mapped to the same scheduled visit, the closer of those values will be considered for summarization. If multiple records exist with the same distance from the target study day, the last occurrence will be used. Visit windows are intended to be contiguous such that all data collected at all post-Baseline visits, whether scheduled or unscheduled, will map to one of the visits.

The visit displayed on data listings will be reflective of the scheduled visit label as reported on the CRF. Study days relative to Baseline will be displayed for each visit so it is apparent which visit the data may have been reassigned to in the summaries.

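### The SAP's relative-day formula gives pre-dose days a positive sign and numbers the first dosing day 0 instead of 1

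*SAP*

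**What the plan says.** SAP Section 9.2.3 introduces the variable: "Analysis relative day is the day relative to the first dosing day". It then gives two branches. The first, analysis date minus first dose date plus 1, applies only "if analysis date is after the first dose date, or else as: first dose date – analysis date" for every remaining date.

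Other parts of the SAP number days differently:

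- Section 7.3 uses negative labels before dosing: "Day -4 through Day -1 representing the Pre-dose Baseline Period (Cu/Mo balance").
- Section 4 places the 15 dosing days on Day 1 to Day 15, so the first dosing day is Day 1.
- Section 9.2.8 states "Baseline will have a target study day of 1".
- Section 7.4.1 computes exposure as "date of last exposure to treatment – date of first dose + 1", which counts the first dosing day as 1.

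On where relative days appear, Section 9.2.8 says "Study days relative to Baseline will be displayed for each visit" on data listings. Section 7.4.3.1 adds, for laboratory results, "All data, including that which is only collected at Screening, will be included in data listings". Section 9.2.3 is the only relative-day formula in the SAP. Section 9.3, which could have qualified it, is marked not applicable.

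**The concern.** Section 9.2 is the part of the SAP that programmers implement, and this rule cannot return a negative day. The first dosing day becomes 0, a day the study does not have, and the value 1 goes to the day before dosing.

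The practical risk is in the listings. If their study days come from Section 9.2.3, pre-dose records carry numbers that look post-dose. Chemistry and hematology are scheduled both at check-in (Day -8) and on Day 8, and both records would show study day 8. Records taken after dosing on Day 1, such as the 4-hour ECG, would show day 0.

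A larger risk arises only if someone used the variable to select the balance periods of Section 7.3. The SAP does not say to do that.

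**Working it through.** **Inputs.** The two branches of SAP Section 9.2.3; the day labels in SAP Sections 4 and 7.3; the screening, check-in, discharge and end-of-study days in Protocol Table 1. The labels have no Day 0, so Day -1 is the calendar day before first dose.

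**Formulas.** Let A be the analysis date and F the first dose date.

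- As written: if A > F, day = A − F + 1; otherwise day = F − A.
- Corrected: if A ≥ F, day = A − F + 1; otherwise day = A − F.

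**Results by day.**

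| Label | A − F | As written | Corrected |
|---|---|---|---|
| Day -35 | -35 | 35 | -35 |
| Day -8 | -8 | 8 | -8 |
| Day -4 | -4 | 4 | -4 |
| Day -3 | -3 | 3 | -3 |
| Day -2 | -2 | 2 | -2 |
| Day -1 | -1 | 1 | -1 |
| Day 1 | 0 | 0 | 1 |
| Day 2 | 1 | 2 | 2 |
| Day 15 | 14 | 15 | 15 |
| Day 30 | 29 | 30 | 30 |

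The SAP's own labels (-4, -3, -2, -1, 1) are not reproduced by the rule as written. They are reproduced by the corrected rule, which matches all 35 + 43 = 78 labels from Day -35 to Day 43.

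**How many days are wrong.**

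- In the unit, Day -8 to Day 31: 8 + 31 = 39 days. Wrong: 8 pre-dose days + Day 1 = 9.
- Intake/output collection, Day -4 to Day 30: 4 + 30 = 34 days. Wrong: 4 pre-dose days + Day 1 = 5.
- Screening Days -35 to -9 become 35 to 9.

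**Collisions.** Among in-unit days, each derived value from 2 to 8 holds one pre-dose day and one treatment day. Among intake/output days this is so for values 2 to 4.

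**Conditional check.** The table below applies only if the variable were used to pick the Section 7.3 periods. It counts intake/output days by derived day.

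| Period | Intended days | As written | Reason |
|---|---|---|---|
| Day -4 to -1 | 4 | 0 | no negative values exist |
| Day 4 to 15 | 12 | 12 + 1 = 13 | Day -4 enters |
| Day 1 to 15 | 15 | 15 − 1 + 4 = 18 | Day 1 lost, Days -4 to -1 enter |
| Day 12 to 15 | 4 | 4 | unchanged |
| Day 1 to 30 | 30 | 30 − 1 + 4 = 33 | Day 1 lost, Days -4 to -1 enter |

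**Visit windows.** The windows in SAP Table 3 are not affected. Baseline is chosen as the last measurement at or before first dose, and the numbered windows start at Day 2, where the formula is right.

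**The case against.** The strongest reply is that no specified analysis is shown to use this variable. Baseline value, treatment-emergent status, concomitant medication, exposure and the PK/PD parameters each have their own date or time rule. The balance periods are given as named days, and Section 7.3 says "The 24-hour collection period is defined as relative to the first ALXN1840 dose administration". All of this stands: no table, endpoint or confidence interval is shown to change.

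The listing harm can also be discounted. Section 9.2.8 puts the CRF visit label on listings, so a check-in record would show its visit name beside the wrong number. The link is also inferred, since Section 9.2.8 speaks of days relative to Baseline and Section 9.2.3 of days relative to first dosing. These points reduce the harm but leave the displayed number wrong if it is derived as specified.

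Two of the supporting comparisons are weaker than the others. The exposure formula is an inclusive duration rather than a day-numbering rule. The Baseline target of 1 is a window anchor for a measurement that may fall on an earlier day. The contradiction with the labels in Sections 4 and 7.3 is enough without them.

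Finally, an empty four-day baseline would be noticed at once in programming, and a programmer would probably apply the usual convention. The programming would then depart from the SAP without any record of why.

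**Conclusion.** The concern holds. Read literally, Section 9.2.3 returns 4 to 1 for Days -4 to -1 and 0 for the first dosing day, against the SAP's own labels, and nothing else in the SAP corrects it. It mislabels 9 of 39 in-unit days and 5 of 34 intake/output days.

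The effect on listings assumes that their study days come from this formula. The effect on the balance periods assumes a use the SAP does not state, so no error in the primary result is claimed. This is a derivation rule that should be corrected, with limited consequences if it is.

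**What to change.** Replace the rule in SAP Section 9.2.3 with: if the analysis date is on or after the first dose date, day = analysis date − first dose date + 1; otherwise day = analysis date − first dose date, which is negative, with no Day 0. Both edits are needed: reversing the subtraction alone would leave the first dosing day at 0.

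An optional second sentence could say that intake, urine and stool are assigned to days by the 24-hour periods anchored on first dose in Section 7.3, not by this calendar-date variable. This only clarifies what the SAP already implies.

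The cost is one corrected sentence and, if wanted, one clarifying sentence. No new data and no operational change are needed.

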9.2.4. Baseline Value

The Baseline value is defined as the last non-missing value collected on or prior to first dose.

9.2.5. Body Mass Index

The BMI is derived as follows: $\text{weight (kg)} / [\text{height (cm)} / 100]^2$

9.2.6. Change From Baseline

Change from Baseline will be calculated as: post-Baseline assessment value – Baseline assessment value when both values are not missing.

Percent change from Baseline is calculated as $(\text{change from Baseline} / \text{Baseline result} * 100)$.

If either the Baseline or the post-Baseline result is missing, the change from Baseline and/or percentage change from Baseline is set to missing. Additionally, if the Baseline is 0, the percentage change from Baseline will be missing.

9.2.7. Medications and Therapies

Medication/therapies with administration dates and times on or after the date and time of the first study drug dose are considered concomitant. If the start date of a medication or therapy is partially or completely missing and the end (stop) date and time of the medication/therapy does not indicate that it occurred prior to first dose, then the determination of concomitant status will be based on the following:

If the start year is after the year of the first study drug dose, then the medication/therapy is concomitant; else, if the start year is the same as the year of the first study drug dose and the start month is missing, then the medication/therapy is concomitant; else if the start month is present and is the same or after the month of the first study drug dose, then the medication/therapy is concomitant; else, if the start date is completely missing, then the medication/therapy is concomitant.

All other medications/therapies are considered prior medications/therapies and could occur from the 14 days prior to study enrollment through the Screening Period and prior to the first dose.

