7.1.4. Prior and Concomitant Medications/Therapies

Prior medications will be defined as medications that were discontinued prior to the start of study drug. Concomitant medications will be defined as medications that either started prior to first dose of study drug and were continuing at the time of first dose of study drug or started on or after the date of the first dose of study drug. If it cannot be determined whether a medication was stopped prior to the start of study drug dosing due to partial or missing medication start or end dates, it will be considered a concomitant medication.

The World Health Organization (WHO) Drug Dictionary version from March 2018 or later will be used to code the medications. Medications will be summarized by Anatomical Therapeutic Chemical (ATC) level 3 class and generic drug name.

Prior and concomitant medications will be summarized separately for the FA Set by group and overall. The number and percentage of participants receiving any concomitant medication will be summarized, as well as the number and percentage receiving any concomitant medication by ATC drug class and generic drug name. Participants reporting use of more than 1 medication at each level of summarization (any medication received, ATC class, and generic drug name) will be counted only once. All ATC class terms will be displayed alphabetically and generic drug names within each ATC class will be displayed by descending order of incidence.

Prior and concomitant medications will be presented in a data listing by participant and medication name.

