9.2. Technical Specifications for Derived Variables

9.2.1. Adverse Events

The analysis of AEs is described in detail in Section 7.4.2.

Treatment-emergent AEs are events with start dates and start times on or after the date and time of the first study drug dose. If the start date of an AE is partially or completely missing and the end (stop) date and time of the AE does not indicate that it occurred prior to first dose, then the determination of treatment-emergent status will be based on the following:

- If the start year is after the year of the first study drug dose, then the AE is treatment-emergent; else,
- If the start year is the same as the year of the first study drug dose and
 - the start month is missing, then the AE is treatment-emergent; else if
 - the start month is present and is the same or after the month of the first study drug dose, then the AE is treatment-emergent; else,
- If the start date is completely missing, then the AE is treatment-emergent.

All other AEs are considered PTAEs (ie, AEs with partial or complete start dates before first study drug dose).

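### The partial-start-date algorithm in SAP 9.2.7 can class as prior a medication that SAP 7.1.4 makes concomitant (minor; medication summaries only)

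*SAP*

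**What the plan says.** SAP 7.1.4 (Prior and Concomitant Medications/Therapies) defines the two categories by stopping: "Prior medications will be defined as medications that were discontinued prior to the start of study drug". Concomitant drugs include those that "started prior to first dose of study drug and were continuing at the time of first dose of study drug". The section also has a default for incomplete dates. If it cannot be established that a drug had stopped before dosing, "due to partial or missing medication start or end dates, it will be considered a concomitant medication". The two categories are summarized separately on the FA Set, and both go into a listing by participant.

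SAP 9.2.7 (Medications and Therapies) opens with: "Medication/therapies with administration dates and times on or after the date and time of the first study drug dose are considered concomitant". It then gives an algorithm for records with a partly or wholly missing start date, which applies when the "end (stop) date and time of the medication/therapy does not indicate that it occurred prior to first dose". Such a record is concomitant in four cases:

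- its start year is later than the dosing year;
- its start year is the dosing year and the month is missing;
- its start month is the dosing month or later;
- its start date is wholly missing.

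The rest are swept up by: "All other medications/therapies are considered prior medications/therapies and could occur from the 14 days prior to study enrollment".

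SAP 9.2.1 (Adverse Events) uses nearly the same sequence of tests for treatment emergence, for example "the start month is present and is the same or after the month of the first study drug dose, then the AE is treatment-emergent".

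**The concern.** Start date is the right test for an adverse event, because onset decides whether the event is treatment-emergent. It is the wrong test for a medication, because a drug begun long before dosing may still be taken during it. The algorithm in 9.2.7 appears to carry the adverse-event logic over, and it applies it to records that have not been shown to have ended before dosing. Those are the records that 7.1.4 sends to concomitant.

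The drugs most exposed are long-running ones that the protocol allows. Exclusion criterion 15 in Protocol 5.2 exempts oral contraceptives and leaves room for prescriptions approved by the sponsor. Protocol 10.4 also accepts implants, hormone-releasing intrauterine systems, injectables and other hormonal methods. What is at stake is whether the concomitant-medication summary counts such drugs. Two programmers working from different sections could produce different tables from the same data.

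**Working it through.** The plan gives no figure to reproduce, so the check runs the same records through both rules. For illustration, assume a first dose on 15 July 2020; the documents give no dosing dates.

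**Rule A (7.1.4).** Prior if known to have stopped before first dose; otherwise concomitant.

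**Rule B (9.2.7).** The four start-date branches, then prior for all others. Its first sentence can be read in two ways:

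- *Narrow:* the dates meant are start dates.
- *Broad:* any administration from first dose onward makes the drug concomitant.

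The month branch is first read as belonging to the dosing year, as its counterpart does in 9.2.1.

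| Start date recorded | Stop date | 7.1.4 | 9.2.7 narrow | 9.2.7 broad |
|---|---|---|---|---|
| May 2020 | ongoing | concomitant | **prior** | concomitant |
| May 2020 | missing | concomitant | **prior** | **prior** |
| Nov 2019 | ongoing | concomitant | **prior** | concomitant |
| Nov 2019 | missing | concomitant | **prior** | **prior** |
| 2019, month unknown | ongoing | concomitant | **prior** | concomitant |
| 2019, month unknown | missing | concomitant | **prior** | **prior** |
| Jul 2020 | ongoing or missing | concomitant | concomitant | concomitant |
| 2020, month unknown | ongoing or missing | concomitant | concomitant | concomitant |
| wholly missing | ongoing or missing | concomitant | concomitant | concomitant |
| any of the above | before first dose | prior | prior | prior |

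Six start patterns by three stop states give 6 × 3 = 18 combinations. The sections disagree on 3 + 3 = 6 of them under the narrow reading and on 3 under the broad reading. These counts describe the logic and are not expected frequencies.

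**Step through one record.** Start May 2020, day unknown, stop date missing:

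1. The start year is not later than 2020.
2. The month is not missing.
3. May is not July or later.
4. The start date is not wholly missing.

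No branch catches it, so 9.2.7 gives prior. The broad reading does not rescue it, because nothing shows an administration after first dose. Under 7.1.4 it cannot be determined that the drug had stopped, so it is concomitant.

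**The month branch.** In 9.2.7 the tests run together in one sentence, so the month test could be read without the same-year condition. November 2019 against a July dose would then be caught as concomitant, leaving 4 conflicts (narrow) or 2 (broad). May 2020 and 2019 with month unknown are still prior, so the conflict remains.

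**An odd consequence.** With a missing stop date, a wholly unknown start date gives concomitant, while a known earlier month gives prior. Knowing more about the start moves the drug out of the concomitant table.

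**After aligning 9.2.7 with 7.1.4.** The sections agree on all 18 combinations. Adding two complete start dates before first dose (3 May 2020 and 3 November 2019) makes 8 × 3 = 24 combinations, and they agree on all of those too.

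**The case against.** The strongest objection is the first sentence of 9.2.7. A drug still being taken at first dose has administrations after it, so on an ordinary reading it is already concomitant before the algorithm is reached. This stands as a possible reading, and it removes the conflict for drugs documented as ongoing. It is not the only reading, because the next sentence expressly takes up records with an incomplete start date and tests only that date. It does nothing for a missing or undetermined stop date.

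A second objection is that 7.1.4 already states the right rule in the main text, and 9.2.7 is a technical appendix that is merely out of step. That is fair, and it makes the correction a matter of consistency. But the SAP gives no order of precedence, and SAP 4.2 says this is the first version, so neither text supersedes the other.

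Three stronger inferences are tempting, and the documents do not support them:

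- *Every ongoing drug with an early partial start date is misclassified.* That holds only under the narrow reading.
- *Readers could not see background therapy during the copper measurements.* Protocol 6.5 requires start and end dates to be recorded, and SAP 7.1.4 requires a prior-medication summary and a listing. A relabelled record changes tables but is not lost.
- *A definite number of participants would drop out of the table.* The documents give no sex ratio, no rate of contraceptive use and no rate of partial dates, so any count would be conjecture.

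**Conclusion.** The inconsistency is real, and its severity is minor. For a partial start date in an earlier month of the dosing year, or in an earlier year that no branch catches, 9.2.7 gives prior where 7.1.4 gives concomitant. With a missing or undetermined stop date this does not depend on interpretation. For a documented-ongoing drug it depends on the narrow reading of the opening sentence.

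The effect stops at the two medication summaries and mainly concerns hormonal contraceptives and any prescriptions approved by the sponsor. The other eligibility restrictions on medication remove most other background drugs. The primary analysis (SAP 7.3.1) is a descriptive change from baseline on the FA Set. Neither the FA Set nor the stated Per Protocol criteria (SAP 6.3 and 6.4) use the prior or concomitant label, and no subgroup or sensitivity analysis is planned (SAP 7.3.1.2 and 7.3.1.5). No copper-balance estimate or confidence limit changes. The number of affected records cannot be derived and may be zero.

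**What to change.** Replace the algorithm in SAP 9.2.7 with the rule of 7.1.4. A medication or therapy is prior only if its stop date, complete or partial, shows that it ended before first dose. Every other record is concomitant, whatever its start date. For a partial stop date, state the test explicitly: the drug is prior only if the latest calendar date compatible with what was recorded falls before first dose. With the illustrative dose of 15 July 2020, a stop recorded as June 2020 is prior, and a stop recorded as July 2020 is undetermined and so concomitant.

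The opening sentence of 9.2.7 should be reworded or dropped so that it no longer admits two readings. The start-date logic of 9.2.1 can stay, since onset is the right test for adverse events.

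The cost is one paragraph of SAP text and simpler programming. It needs no new data and is best done before the medication tables are programmed and the database is locked.
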